Highly active anti-retroviral therapy (HAART) has been successful in controlling viral replication and decreasing levels of virus in plasma to levels below limits of detection as determined by commercially available assays in most human immunodeficiency virus (HIV)-infected individuals (1-3). Even in individuals who have been treated for considerable periods of time and whose plasma virus levels remain below detectable, replication-competent HIV can be invariably isolated from latently infected, resting CD4+ T cells (4-6). This observation, and the common experience of viral rebound among HIV-infected individuals in whom HAART has been discontinued (7), as well as the fact that this pool of latently infected cells is long-lived and does not decay substantially over time (4, 5), have led to the recognition that these cells constitute a principal impediment to the “cure” of HIV infection (4-6, 8-10).

A variety of cytokines, including interleukin (IL)-2, tumor necrosis factor (TNF)- α IL-15 and IL-6 can induce *in vitro* the expression of HIV from latently infected, resting CD4+ T cells obtained from HIV infected individuals (11). Thus, it has been proposed that latent HIV might be deliberately ‘purged’ by treating infected individuals simultaneously with HAART and agents that activate cells to express HIV (8-10, 12). After being activated, these latently infected cells may die from cytopathic effects and/or immune effector mechanisms, whereas HAART would prevent new rounds of infection mediated by the replication competent viruses expressed by activation from latency (8-10, 12).

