The purpose of this pilot study is to observe the effects of up to eight 8-weekly cycles of subcutaneous recombinant interleukin-2 (SC rIL-2) on levels of replication-competent HIV in blood CD4 T cells in 20 participants with chronically suppressed HIV infection (viral load <50 copies/mL) who are stable on the same ART regimen for at least one year and have a CD4 T cell count ≥ 350 cells/mm³. We hypothesize that IL-2 administration will result in a reduction of the replication-competent reservoir, as measured by the QVOA assay, compared to the baseline values in this population.

B.1. STUDY ENDPOINTS AND OUTCOME MEASURES

The primary endpoint of the study is the change in the level of replication-competent virus from baseline to the end of rIL-2 treatment, as measured by the Quantitative Viral Outgrowth Assay (QVOA).

B.2. PRIMARY OBJECTIVE

The primary objective will be to compare levels of replication competent HIV in circulating CD4 T cells before and after up to 8 cycles of rIL-2 administration. The frequency of CD4 T cells containing replication-competent virus in leukapheresis samples obtained at baseline and at the end of rIL-2 treatment will be enumerated using several state of the art methods. The primary readout for this objective will be measurement of replication-competent virus by Quantitative Viral Outgrowth Assay (QVOA) performed by [name]'s group at Accelevir.

B.3. SECONDARY OBJECTIVES

- 1) To examine the relationships between levels of replication competent HIV as identified by QVOA and other measures of HIV persistence:
 - a) the intact proviral DNA assay ([name]),
 - b) the Envelope Detection by Induced Transcription-based Sequencing (EDITS, [name]) performed on the same pre-trial and post-trial leukapheresis samples.
- 2) To explore the effects of rIL-2 administration on induction of HIV expression in vivo as measured by the EDITS assay and plasma HIV levels.
- 3) To examine the effects of rIL-2 administration on natural killer cell phenotype and function and on the ability of NK cells to limit HIV propagation in vitro.

C. METHODS

C.1. STUDY DESIGN

This is an open label pilot study of 20 participants with chronically suppressed HIV infection (viral load <50 copies/mL), stable on an ART regimen for at least one year, who have a CD4 T cell count ≥ 350 cells/mm³. All participants will receive rIL-2.

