All participants will receive rIL-2, 5 million units (MU) subcutaneously (SC) twice a day \times 4 consecutive days, every 8 weeks, for 8 cycles in addition to ART.

Ideally, rIL-2 doses should be 10 – 12 hours apart, but no closer than 6 hours, and no greater than 18 hours apart.

If at any point rIL-2 is discontinued, efforts will be made to maintain follow-up for all data collection as outlined in the schedule of events.

C.2. STATISTICAL CONSIDERATIONS

C.2.1. Analytic Plan

The primary analysis will test whether the change in the size of the replication-competent reservoir, as measured by the modified QVOA assay, from baseline to two weeks after the last rIL-2 infusion is significantly different than is expected by random variation. In this intent-to-treat analysis, all participants who received at least one dose of IL-2 will be included. Secondarily, we will perform an on-treatment analysis including only the subset of participants who received all eight planned IL-2 cycles. We will use mixed effects models to estimate the effect of IL-2 treatment on the replication-competent reservoir among all participants, controlling for possible confounding factors including at a minimum CD4 T cell count at baseline and at pre-ART nadir, duration of virologic suppression, type of antiretroviral regimen at study entry, historical peak plasma HIV RNA, and demographic factors.

We will then fit the relevant models to address the following secondary objectives:

- a. Replicate the analyses above in the on-treatment population, i.e., those who received all 8 planned IL-2 cycles.
- b. In the intent-to-treat population, add a term indicating the number of IL-2 cycles each participant received. This will account for variability of total dose, and the associated parameter and its interaction to time point will provide an estimation of the effect modification expected from repeated dosing. We will assess for non-linearity of any dose effect both graphically and formally, and fit higher-order terms as suggested by those analyses, to explore whether there is a threshold effect (i.e., whether the effect size changes drastically past a given number of doses), an analysis that was not reported in the original Chun paper.

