3. HIV-1 infection, documented by and FDA-approved ELISA, EIA, or rapid antibody detection method, and confirmed by a second approved antibody-based test or by a positive approved HIV RNA detection assay.
4. CD4+ T cell count ≥ 350 cells/mm 3 .
5. HIV-1 RNA < 50 copies/mL obtained within 60 days prior to study entry performed with an FDA-approved HIV-1 RNA assay.
6. Adequate venous access and no other contraindications for leukapheresis.
7. Absolute neutrophil count (ANC) ≥ 1500 /mm 3 .
8. Hemoglobin level >10 g/dL.
9. Platelet count $\geq 100,000$ /mm 3 .

² Accelevir, data on file

10. Serum creatinine ≤ 1.5 mg/dL
11. AST and ALT < 2.5 times the upper limit of normal
12. TSH, T3, and T4 levels within the normal range of the processing laboratory.
13. Anti-thyrosine peroxidase (TPO) antibodies within the normal range of the processing laboratory.
14. Willing to comply with study-mandated evaluations; including not changing antiretroviral regimen (unless medically indicated) during the study period.
15. All participants must have received HAART, and had viral loads below the limit of quantification of the assay for at least 1 year. Participants who had intermittent isolated episodes of detectable low-level viremia < 500 copies RNA/mL flanked by viral loads below the limit of quantification of the assay will remain eligible.
16. On a stable combination antiretroviral regimen (no changes to treatment within 4 weeks of enrollment) including at least 3 medications and willing to continue on current antiretroviral therapy for the duration of the study, unless otherwise medically indicated.

C.4. EXCLUSION CRITERIA

1. Childbearing potential for female participants. For the purposes of this study, a woman is considered to be of childbearing potential if she is not postmenarchial, has not had a documented surgical sterilization procedure, has an intact uterus and at least 1 ovary, and has had a spontaneous menstrual period in the last 2 years.
2. Acute or chronic hepatitis C infection, defined as a positive plasma HCV RNA using any FDA-approved qualitative or quantitative test in a participant with a positive HCV antibody (HCV RNA testing is not required in participants with a negative HCV antibody). Participants who have completed a course of a direct-acting antiviral agent for hepatitis C and have a confirmed plasma HCV RNA level below the limit of detection of the assay 12 weeks or longer after completion of therapy will be eligible.

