The screening visit will occur 8-16 weeks prior to start of rIL-2 treatment, and will include:

- History and complete physical examination that includes evaluation of adequate venous access for leukapheresis
- Height and weight measurements
- Concomitant medication review
- CBC and metabolic panel
- Pregnancy test
- Thyroid function tests and anti-Tpo antibodies
- CD4+ and CD8+ T cell count (both absolute and as percent of lymphocytes).
- Plasma HIV RNA level (using the locally available assay) and verification that plasma HIV RNA levels prior to screening meet the inclusion criteria.
- Hepatitis B and C testing
- Informed consent

D.2.2. Leukapheresis Visit

The pre-treatment leukapheresis visit will occur 4-8 weeks prior to start of rIL-2 treatment, and will include:

- Interval history and targeted physical examination
- Concomitant medication review.
- CBC and metabolic panel
- CD4+ and CD8+ T cell count (both absolute and as percent of lymphocytes) and documentation of all interim CD4+ counts (absolute and percents).
- Thyroid function tests and anti-Tpo antibodies.
- Participant will be instructed as to how IL-2 will be injected subcutaneously. Instructions for preparing rIL-2 for administration are given in the Manual of Operations, which includes the Investigator's Brochure as an appendix. Participants receiving rIL-2 will be taught to give themselves injections. Participants will be given a dosing log for future use and will be encouraged to refer to it during their daily activities. Supporting materials for clinical staff and for participants on administering rIL-2 and managing expected side effects are included in the Manual of Operations. The Manual of Operations also includes contact information for questions concerning clinical management. No rIL-2 will be administered at this visit.
- A 4 liter leukapheresis will be performed at the Seidman Ambulatory Stem Cell Transplant

Unit at University Hospitals using AIDS protocol 328.

- Plasma will be frozen for single copy HIV RNA assay.
- Leukapheresis samples will be processed into PBMC that will be cryopreserved for assays of:
 - HIV reservoir by QVOA
 - HIV reservoir by EDITS
 - Total and intact proviral DNA assay (Accelavir)
 - Immune Cell Phenotype
 - NK cell phenotype

D.2.3. rIL-2 Initial Treatment Visit – Cycle 1, Day 0

The first IL-2 cycle will start 4-8 weeks after the leukapheresis visit and will include:

- Interval history and targeted physical examination, including weight.

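### With one arm and a single QVOA sample before and after treatment, the primary analysis cannot separate an rIL-2 effect from change over time on ART

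*Combined protocol and SAP*

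**What the plan says.** Section B states the hypothesis as a before-and-after comparison: "We hypothesize that IL-2 administration will result in a reduction of the replication-competent reservoir, as measured by the QVOA assay, compared to the baseline values". Section C.1 has no comparator ("All participants will receive rIL-2"), with treatment "every 8 weeks, for 8 cycles in addition to ART".

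The primary test in C.2.1 asks whether the change in QVOA "is significantly different than is expected by random variation". The same paragraph then interprets the result: "We will use mixed effects models to estimate the effect of IL-2 treatment on the replication-competent reservoir among all participants". The adjustment covariates are CD4 count at baseline and at nadir, duration of suppression, regimen type at entry, historical peak HIV RNA and demographics.

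QVOA is scheduled twice. D.2.2 places the first sample: "The pre-treatment leukapheresis visit will occur 4-8 weeks prior to start of rIL-2 treatment". D.2.10 places the second at 8 weeks, plus or minus 2, after day 0 of cycle 8. For early stoppers it is 6 to 10 weeks after day 0 of their last cycle.

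On background decline, A.1 says only that "this pool of latently infected cells is long-lived and does not decay substantially over time". It gives no rate, and the analysis makes no use of the statement. The minimum prior suppression, in C.3 item 15, is one year: "All participants must have received HAART, and had viral loads below the limit of quantification of the assay for at least 1 year".

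**The concern.** The null hypothesis is no change apart from noise. A systematic decline on continued ART is not noise, so the test would count it as evidence against the null, and the model would report it as an effect of IL-2. If such a decline occurs, it runs in the direction of the hypothesis.

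This matters because A.2 sets out to confirm a cross-sectional study whose contrast was IL-2 plus ART against ART alone. That contrast had a concurrent ART-only group. The present one has only each person's own baseline, so a significant fall here would not by itself confirm the source finding. Adjusting for a list of possible confounders may suggest that the problem has been handled, when the main alternative explanation, time, is not on the list.

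**Working it through.** **1. The plan's own figure.** C.2.2 gives 80% power with 20 participants for a change of 0.64 IUPM at variance 0.41. The synopsis gives the same power and confidence interval with 16. Alpha and the within-person correlation are not stated, so I assume a two-sided 5% test and independent samples. The SD of the change is then √(2 × 0.41) = 0.906.

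- N = 16: SE = 0.906/√16 = 0.226, and 0.64/0.226 = 2.83. Power is 0.81 (normal) or 0.75 (t).
- N = 20: SE = 0.906/√20 = 0.202, and 0.64/0.202 = 3.16. Power is 0.89 (normal) or 0.85 (t).

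The synopsis figure reproduces under the normal approximation; the C.2.2 figure does not reproduce in either form. That discrepancy is a separate matter. What counts here is that 0.64 is a difference between two groups in the source study, reused as an expected change from baseline. That reuse assumes zero background change.

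**2. Time between the two QVOA samples** (D.2.2, D.2.5 to D.2.8, D.2.10). Baseline is 4 to 8 weeks before cycle 1, cycles are 7 to 10 weeks apart, and the final sample is 6 to 10 weeks after day 0 of the last cycle.

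- Eight cycles: minimum 4 + 7 × 7 + 6 = 59 weeks; maximum 8 + 7 × 10 + 10 = 88 weeks. Nominal: (4 to 8) + 7 × 8 + 8 = 68 to 72 weeks.
- One cycle: 4 + 6 = 10 weeks to 8 + 10 = 18 weeks.
- Seven cycles: 4 + 6 × 7 + 6 = 52 weeks to 8 + 6 × 10 + 10 = 78 weeks.

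C.2.1 instead puts the final time point two weeks after the last rIL-2 administration, about 17 days after day 0 of the last cycle. For completers that gives 4 + 49 + 2.4 = 55 to 8 + 70 + 2.4 = 80 weeks. C.2.1 and D.2.10 conflict and must be reconciled; the point below holds under either.

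**3. Aliasing.** Everyone is untreated at the first sample and treated by the second, so the indicators for treatment and for time point are the same column. A design matrix with 20 participant effects, time point, treatment and two covariate-by-time terms has 24 columns and rank 23. Removing the treatment column leaves the rank at 23. Covariates entered as main effects describe differences between people: in a simulated two-time-point mixed model, the estimated change was -0.3129 (SE 0.087) both with and without them.

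**4. Secondary models.** Model (b) adds the number of cycles and its interaction with time point. Each further cycle adds 7 to 10 weeks, so cycles and elapsed time rise together, and background decay alone could look like a dose response. Model (d) adjusts for time-updated CD4 count, which addresses dilution and leaves decay on ART untouched.

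**5. Possible size.** The documents give no decay rate, so the falls below are assumptions. The rejection probability comes from the noncentral t distribution with 19 degrees of freedom and noncentrality fall/SE, for 20 pairs and no drug effect. Samples are taken as independent, and the same fall is applied to all 20 participants. SE = √(2 × 0.41)/√20 = 0.202 for variance 0.41, and √(2 × 0.11)/√20 = 0.105 for variance 0.11, the figure C.2.2 suggests for the optimized assay.

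| Assumed background fall (IUPM) | Share of the 0.64 target | Significant, variance 0.41 | Significant, variance 0.11 |
|---|---|---|---|
| 0 | 0% | 5% | 5% |
| 0.1 | 16% | 8% | 15% |
| 0.2 | 31% | 16% | 44% |
| 0.3 | 47% | 29% | 77% |

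A more precise assay makes a given drift more likely to reach significance.

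**6. The same question in half-lives.** Proportional fall = 1 - 0.5^(w/(52.18 × H)), with w in weeks and H in years. Over 59 to 88 weeks, assumed half-lives of 2, 4, 8 and 16 years give falls of 32 to 44%, 18 to 25%, 9 to 14% and 5 to 7%. Over 10 to 18 weeks, a 2-year half-life gives only about 6 to 11%. The plan states no expected baseline QVOA level, so these percentages cannot be converted to IUPM.

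**The case against.** The sponsor can fairly say that this is an open-label pilot, that its hypothesis is explicitly relative to baseline, and that the test is worded as a difference in either direction. A.1 regards decay as slight. If it is, the inflation is small: about 8% against 5% for a fall of 0.1 IUPM at the planning variance. Model (b) carries some information, because D.2.13 allows cycles to be cancelled or delayed, so cycle count and elapsed time need not move in perfect step. The covariate list is a minimum and could include interactions with time.

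Most of this bears on size. The information in model (b) is weak and non-randomised, and interactions with time still leave the average change aliased with treatment. The reading as a drug effect comes from C.2.1 itself.

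Three stronger readings are tempting and are not supported:

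- *That all pairs are 59 to 88 weeks apart.* This holds for eight-cycle completers seen within the windows. The primary population is everyone with at least one dose. Delays under D.2.12 and D.2.13 also mean that 88 weeks is not a firm maximum.
- *That false-positive rates reach about 80%.* A 2-year half-life with an SD of 0.3 for the log10 change gives 81%. The plan names no log10 scale, that SD has no source in the documents, and a half-life so short sits badly with A.1.
- *That a background decline has been shown.* A.1 rules out a substantial one in the authors' view and leaves a smaller one open. It establishes neither its presence nor its size.

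**Conclusion.** The concern holds as a limit on what the primary analysis can show. In this design the change in QVOA estimates rIL-2 and elapsed time on ART together, and nothing in C.2.1 separates an average background decline from a drug effect. That conclusion follows from the design and needs no assumption about decay.

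The size of any bias is unknown. Over assumed falls of 0.1 to 0.3 IUPM, the chance of a significant result with no drug effect is about 8 to 29% at variance 0.41 and 15 to 77% at variance 0.11. These figures rest on 20 complete pairs, independent samples, a two-sided 5% test and a common fall. They would be lower if many participants stopped early and so had short intervals, and higher if repeat samples from one person were positively correlated. The trial can still report a change from baseline. It should not report that change as an rIL-2 effect without a stated condition on background decay.

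**What to change.** In C.2.1:

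1. State that the before-and-after change and its 95% CI estimate rIL-2 plus time on ART.
2. Prespecify a sensitivity analysis that subtracts an assumed background decline, over a stated range of half-lives starting at no decay (for example none, 16, 8, 4 and 2 years). Compute the decline from each participant's actual interval between samples, on the scale chosen for the primary analysis.
3. Report the tipping point: the half-life at which the CI no longer excludes background decline.
4. Word any attribution to rIL-2 as conditional on background decay slower than that tipping point.
5. Reconcile the final time point in C.2.1 with the visit window in D.2.10, since the interval enters the calculation.

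An interaction of suppression duration with time point would not serve as the remedy. It describes how the change varies between people, leaves the average change aliased, and spends a parameter with only 20 participants.

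The cost is some wording and one table, with no new patients or samples. The downside is that a modest fall will support a weaker claim.

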18. Current continued use, or anticipated continued medical indication for hepatotoxic agents, including but not limited to amiodarone, methotrexate, and anticonvulsants and antimicrobials with elevated hepatotoxic potential.
NOTE: Low doses or limited duration of these agents (i.e., ≤ 14 days) is not exclusionary.
19. Active drug or alcohol use or dependence that, in the opinion of the investigator, would interfere with adherence to study requirements.
20. Serious illness requiring systemic treatment and/or hospitalization within 30 days prior to study entry that in the judgement of the investigator may compromise study participation or pose additional risks to the participant.
21. Any other condition that, in the opinion of the clinical investigator or sponsor, might compromise any aspect of this trial.

C.5. STUDY TREATMENT PLAN

C.5.1. Study Medication (rIL-2)

Proleukin® (Prometheus Laboratories) is provided as a sterile, white to off-white, lyophilized cake in glass vials, each containing 22 MIU.

C.5.1.1. Dosage and Cycle Guidelines

Participants will receive rIL-2 at an initial dose of approximately 5 MIU twice daily for 4 consecutive days every 8 weeks (8 cycles total). Each vial will be reconstituted according to the package insert instructions using 1.2 mL of diluent, and 4 doses will be obtained from each vial. Occasionally, the reconstituted volume that can be drawn from the vial may result in doses that are slightly smaller than 5 MIU each. These small deviations from the total intended dose are biologically inconsequential and do not constitute protocol deviations.

C.5.1.2. Preparation of rIL-2 for Subcutaneous Administration

The Investigational Pharmacy will reconstitute rIL-2 at the beginning of each cycle for each participant, and draw each individual dose into tuberculin syringes under sterile conditions. As was done in two previous large trials of rIL-2 in HIV-infected participants(19), all eight doses will be prepared, labeled, and delivered to the participant on day 0 of each cycle. This procedure may be modified in the course of

the study if deemed necessary by the Investigational Pharmacy, the investigators, or a regulatory authority, including the option to prepare a smaller number of doses in advance. In that case, pre-filled syringes may be shipped by fast courier to the participant's residence.

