Participants will be taught to give themselves rIL-2 injections. This will require substantial clinician support in terms of both time spent instructing participants and in availability to answer participant questions and respond to participant concerns about injections and side effects. Refer to the Manual of Operating Procedures (MOPS) document for further details on initial and subsequent dose administration

C.5.2. Guidelines for Dosage Modification

Participants will be monitored closely for side effects of rIL-2. Participants who experience dose-limiting side effects may have their rIL-2 temporarily interrupted or their dose reduced.

The Manual of Operations (MOPs) includes a list of toxicities for which the investigator may choose to temporarily interrupt or dose-reduce rIL-2 (hereinafter, dose-limiting toxicities). An outline of criteria for certain specific potential adverse events are provided in section E.1. Briefly, the following guidelines apply:

- For toxicities during the 4-consecutive-day administration of rIL-2 that are considered dose-limiting, the remaining rIL-2 doses of that cycle of therapy will be interrupted until the dose-limiting toxicity is no longer considered dose-limiting.
- In some circumstances, a toxicity may be regarded as dose-limiting in the opinion of the investigator, even if it does not meet the above-mentioned criteria. In these instances, the clinical judgment of the investigator takes precedence.
- When rIL-2 treatment is reinitiated after interruption because of a dose-limiting toxicity, the dose will be reduced by up to 1.5 MIU per injection (3 MIU/day). If the reduced dose results in a dose-limiting toxicity during the same cycle, rIL-2 therapy will again be interrupted. Further dose reduction, if necessary, will be made in the same fashion.
- If a participant cannot tolerate an rIL-2 dose of 2 MIU twice a day then rIL-2 therapy will be permanently stopped.
- If, after a dose reduction, a participant completes a treatment cycle without significant toxicity, then escalation of the rIL-2 dose at the next cycle may occur by an increment of up to 1.5 MIU/dose (3 MIU/day).
- The total duration of a course of rIL-2 will not be extended for doses missed as a result of toxicity or any other reason.

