Medication Category	Timeframe
Antiretroviral medications	Complete history
Immune-based therapies	Within 90 days prior to study entry
Vaccines	Within 30 days prior to study entry
All other prescription and non-prescription medications	Within 90 days prior to entry

D.3.4. Clinical Assessments

D.3.4.1. Complete Physical Exam

A complete physical exam is to include at a minimum an examination of the skin, head, mouth, and neck; auscultation of the heart and lungs; abdominal exam; and examination of the lower extremities for edema. The complete physical exam will also include vital signs (temperature, heart rate, respiration rate, and blood pressure).

D.3.4.2. Targeted Physical Exam

A targeted physical exam is directed to the site or organ system involved in any previously identified or new signs or symptoms that the participant has experienced since the last visit. This exam also includes vital signs (temperature, heart rate, respiration rate, and blood pressure).

D.3.4.3. Height

Height without shoes in centimeters will be obtained at screening and recorded on the CRF at entry.

D.3.4.4. Weight

Weight without shoes in kilograms will be obtained at screening, leukapheresis visit, at

entry and at day 0 of each cycle. The weight obtained at entry and at day 0 of each cycle will be recorded on the CRF.

D.3.4.5. Interval History

At entry, all signs and symptoms, regardless of grade, that occurred within 45 days before entry will be recorded in the source documents. Post-entry, only grade ≥ 2 signs and symptoms, or those that led to a change in treatment, regardless of grade, will be recorded on the corresponding CRFs.

D.3.4.6. Diagnoses

After study entry, all new diagnoses established while on study will be recorded on the source document. Any gradable diagnoses that meet AE criteria will be recorded on the CRF, and relationship to study agent will be assessed.

D.3.4.7. Concomitant Medications

Concomitant prescription or over-the counter medications initiated or discontinued since the last visit will be recorded on the source documents.

D.3.4.8. Study Treatment Modifications

All study drug modifications, including actually administered doses preceding each of the scheduled in-person or phone assessments will be recorded. Any permanent discontinuation of treatment will be recorded on the CRF.

D.3.4.9. Antiretroviral Medications

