To minimize the risk of a severe, immediate-type hypersensitivity reaction or capillary leak syndrome, the first dose of study agent will be administered in the Special Immunology Unit by personnel with experience administering rIL-2 to over 50 participants in the SILCAAT and ACTG 328 trials. Participants will be monitored for a minimum of 30 minutes following the first dose of study drug by personnel with life support training and access to adequate life support equipment and resuscitation medication.

Development of a grade ≥ 3 hypersensitivity reaction, a grade 2 hypersensitivity reaction that includes manifestations of angioedema, or suspected or confirmed capillary leak syndrome will require permanent treatment discontinuation.

E.1.3. Neutropenia

Participants who develop neutropenia will be referred for treatment by a qualified healthcare professional. Volunteers with an ANC $< 2,000$ cells/mm 3 at screening will be excluded.

- Should the ANC decrease to ≥ 500 but $\leq 1,000$ cells/mm 3 , the rIL-2 dose will be interrupted until the ANC is $> 1,000$ cells/mm 3 and then rIL-2 will be restarted at 3.5 million units twice daily. If the ANC then remains above 1,000 cells/mm 3 , this dose will be continued until the end of study.
- If the ANC drops to ≥ 500 but $\leq 1,000$ cells/mm 3 while on the reduced dose of 3.5 million units twice daily, rIL2 will be discontinued until the ANC reaches 1,000 cells/mm 3 , and then resumed at a dose of 2 million units twice daily. If the ANC then remains above 1,000 cells/mm 3 , this dose will be continued until the end of study. If the ANC falls again to $\leq 1,000$ cells/mm 3 while on the reduced 2 million unit twice daily dose, rIL2 will be permanently discontinued.
- Should the ANC decrease to < 500 cells/mm 3 , rIL-2 will be permanently discontinued.

E.1.4. Thrombocytopenia

Participants who develop thrombocytopenia will be referred for treatment by a qualified healthcare professional. Volunteers with platelet counts $< 150,000$ /mm 3 will be excluded.

- Should the platelet count decrease to $\geq 50,000$ but $\leq 100,000$ /mm 3 the rIL-2 dose will be interrupted until the platelet count is $> 100,000$ /mm 3 and then rIL-2 will be restarted at 3.5 million units twice daily. If the platelet count then remains above 100,000 /mm 3 , this dose will be continued until the end of study.

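### The cycle count in C.2.1 item b does not account for total dose: a score of 8 cycles can stand for anything from 320 MIU down to 132.5 MIU with every injection given

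*Combined protocol and SAP*

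**What the plan says.** C.2.1 item b is a secondary analysis in everyone who received at least one dose. Its instruction is to "add a term indicating the number of IL-2 cycles each participant received", and it says of that term: "This will account for variability of total dose". The term and its interaction with time point are then read as effect modification from repeated dosing. Non-linearity is to be examined, including "whether the effect size changes drastically past a given number of doses". So the term counts cycles, the claim is about total dose, and the threshold is expressed in doses.

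Other sections let the size of a cycle vary:

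- C.5.1.1 sets the starting dose at about 5 MIU twice daily for four days, for eight cycles.
- C.5.2 allows repeated reductions of up to 1.5 MIU per injection, with 2 MIU twice daily as the last level before stopping. It also allows the dose to go back up at the next cycle. On lost injections it says: "The total duration of a course of rIL-2 will not be extended for doses missed as a result of toxicity or any other reason".
- E.1.3, E.1.4, E.1.5 and E.1.7 name the levels for neutropenia, thrombocytopenia, AST/ALT and creatinine. In E.1.3, for example, "rIL-2 will be restarted at 3.5 million units twice daily" is the first step and 2 million units twice daily the second.

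The on-treatment set in C.2.1 is also defined by eight cycles, with no dose criterion. I found no rule for when a partly given cycle counts as received, and no model that uses administered MIU. The data to build one will exist, because D.3.4.8 states: "All study drug modifications, including actually administered doses preceding each of the scheduled in-person or phone assessments will be recorded".

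**The concern.** A count of cycles measures total dose only if every cycle delivers about the same amount, and this protocol is written so that cycles need not. Two participants with the same score can differ widely in drug received, and one with fewer cycles can have received more. The dose slope and the search for a threshold would then rest on a mis-scored exposure. With up to 20 participants, a few mis-scored people can move a slope or suggest a threshold that is not there.

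The documents themselves treat dose as mattering. A.4 reports larger CD4 rises at 7.5 than at 1.5 MIU, and I.6.1 justifies eight cycles by matching the exposure in the earlier cross-sectional IL-2 study. The tolerance in C.5.1.1 covers only small shortfalls in the volume drawn from a vial. It does not cover reductions to 3.5 or 2 MIU.

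**Working it through.** The plan states no total dose in MIU, so there is no figure to reproduce. What follows is arithmetic on its own schedule.

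**Inputs.** Starting dose 5 MIU, two injections a day, four days, eight cycles (C.1, C.5.1.1). Reduced levels 3.5 and 2 MIU (E.1, consistent with the 1.5 MIU step in C.5.2).

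**Formula.** Cumulative dose = sum over cycles of (MIU per injection × injections given).

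**Planned course.** 2 × 4 = 8 injections per cycle, and 8 × 8 = 64 in all. Dose per full cycle is 8 × 5 = 40 MIU, and the total is 64 × 5 = 320 MIU.

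**Courses that all score 8, with all 64 injections given:**

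- One step down from cycle 2: 40 + 7 × (8 × 3.5) = 40 + 196 = 236 MIU, or 74% of plan.
- Step down at cycle 2 and again at cycle 3: 40 + 28 + 6 × (8 × 2) = 40 + 28 + 96 = 164 MIU, or 51%. 320 / 164 is about 2-fold, and 164 / 40 = 4.1 full-dose cycles.
- Lower bound, with both step-downs straight after the first two injections: 5 + 3.5 + 62 × 2 = 132.5 MIU, or 41%. 320 / 132.5 = 2.4-fold.

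**Reversed order.** Five full-dose cycles give 5 × 40 = 200 MIU, more than the 164 MIU above. The model scores them 5 and 8.

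**What widens or narrows the spread.** Missed injections widen it. If, as an assumption for illustration, half the injections were missed in eight cycles at 5 MIU, the total would be 8 × 4 × 5 = 160 MIU, still scored 8. Re-escalation under C.5.2 narrows it. One cycle at 3.5 MIU and a return to 5 MIU gives 40 + 28 + 6 × 40 = 308 MIU.

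**Elapsed time between samples.** Baseline leukapheresis is 4-8 weeks before cycle 1 (D.2.2), cycles start 7-10 weeks apart (D.2.5, D.2.7, D.2.8), and the final sample is 6-10 weeks after day 0 of the last cycle (D.2.10).

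- Three cycles: 4 + 2 × 7 + 6 = 24 to 8 + 2 × 10 + 10 = 38 weeks.
- Seven cycles: 4 + 6 × 7 + 6 = 52 to 8 + 6 × 10 + 10 = 78 weeks.
- Eight cycles: 4 + 7 × 7 + 6 = 59 to 8 + 7 × 10 + 10 = 88 weeks.

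Adjacent counts overlap heavily; distant counts do not overlap.

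**Passages to reconcile.** I.6.1 describes five-day cycles, which would make the planned total 5 × 2 × 5 × 8 = 400 MIU rather than 320. C.5.2 permits re-escalation, whereas E.1 continues a reduced dose to the end of study. Both affect how exposure is computed, and the sponsor must reconcile them.

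**The case against.** The strongest defence is that cycle number is a legitimate scale for part of what item b asks. The item speaks of repeated dosing, A.2 describes the motivating study by its average number of cycles, and the count does register stopped and cancelled cycles. Nothing in the documents says that MIU add up across cycles, so a conversion into full-dose equivalents is arithmetic and not pharmacology. Reductions also follow toxicity, so cumulative MIU is no more randomised than cycle count. All of this stands. It argues for keeping cycle count beside a dose term, but it does not make the sentence about total dose true.

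Four stronger readings are tempting and are not supported:

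- A reader might infer that eight complete cycles could all be given at 2 MIU (64 × 2 = 128 MIU, 2.5-fold) or all at 3.5 MIU (224 MIU). Everyone starts at about 5 MIU, so a full 64-injection course cannot follow either schedule. Even 132.5 MIU is a bound. Scheduled safety bloods fall on day 0 of each cycle and on day 7 of cycles 1, 4 and 8, so a laboratory-driven reduction would more plausibly begin at cycle 2, which makes 164 MIU the more realistic extreme.
- A reader might infer that dose cannot be separated from elapsed time. The 52-78 and 59-88 week ranges for seven and eight cycles overlap, and D.2.13 allows cancelled cycles. The correlation over the whole range of counts is real, but cumulative MIU shares it, so changing the term does not remove it. A.1's premise that the latent pool does not decay substantially limits the consequence.
- A reader might infer that the slope will be biased towards zero. When reductions depend on how the participant responds, the direction is unknown.
- A reader might infer that the primary result is affected. It is not, because item b is a later exploratory model.

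**Conclusion.** The stated property is false. Under the protocol's own rules, the number of cycles does not account for variability in total dose. With every injection given, one score of 8 covers 132.5 to 320 MIU (2.4-fold). A step-down at cycles 2 and 3 gives about a 2-fold difference and reverses the ranking against five full cycles. These figures assume four-day cycles and the 5, 3.5 and 2 MIU levels named in E.1.

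The effect on the estimate cannot be sized, because the documents give no frequency of reduced or missed doses. If these are rare, the two scales will nearly agree. The point is confined to item b and to how the eight-cycle on-treatment set is described. It is worth correcting because the remedy uses data already planned.

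**What to change.** In C.2.1 item b:

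- Fit cumulative MIU administered as the total-dose term, derived from the doses recorded under D.3.4.8 and the participant dosing log (D.2.2, D.2.3).
- Keep cycle count as a separate term or a parallel model for the repeated-dosing question, and define when a partly given cycle counts as received.
- Correct the sentence on total dose so that it refers to MIU.
- Name one scale for the threshold analysis, in place of the present mix of cycles and doses.
- Report the median and range of MIU received in the eight-cycle on-treatment set.
- State that both exposure measures are non-randomised, because reductions follow toxicity, and that both rise with elapsed time. Report weeks between the baseline and final samples as description.

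No dosing rule or study procedure changes. The cost is plan wording, a little more analysis work, and one more exploratory model in a sample of up to 20, which should be labelled as such.
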